Appendix 1 **Criteria for Identifying Vital Signs and Weight of Potential Clinical Relevance**

Variable	Criterion Value ^a	Change Relative to Baseline ^a
Pulse Rate	> 120 bpm < 50 bpm	≥ 15 bpm increase ≥ 15 bpm decrease
Systolic Blood Pressure	> 180 mmHg < 90 mmHg	≥ 20 mmHg increase ≥ 20 mmHg decrease
Diastolic Blood Pressure	> 105 mmHg < 50 mmHg	≥ 15 mmHg increase ≥ 15 mmHg decrease
Orthostatic Hypotension	≥ 20 mmHg decrease in systolic blood pressure and a ≥ 25 bpm increase in pulse rate from supine to sitting/standing	Not Applicable
Weight	-	≥ 7% increase ≥ 7% decrease

^aIn order to be identified as potentially clinically relevant, an on-treatment value must meet the “Criterion Value” and also represent a change from the subject’s baseline value of at least the magnitude shown in the “Change Relative to Baseline” column.

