- Patients with type 2 diabetes mellitus who have not been maintained on a stable regimen of anti-diabetic medication(s) or undergone diet/exercise therapy for at least 28 days prior to screening
- Patients meeting either of the following criteria for poor blood glucose control at screening (assessed based on results from the central laboratory)
 - a) Glycosylated hemoglobin (HbA1c) of \geq 7.0% according to the global standard value [NGSP value]
 - b) Fasting blood glucose level of \geq 126 mg/dL or nonfasting blood glucose level of \geq 200 mg/dL
- 16) Patients with substance abuse or substance dependence, including alcohol and benzodiazepines, based on DSM-5 diagnostic criteria within 180 days prior to informed consent; caffeine and nicotine are not included
- 17) Patients with a complication of hypothyroidism or hyperthyroidism at informed consent (excluding those in a

- stable condition due to medications for the previous 90 days or longer at acquisition of informed consent), or abnormal thyroid stimulating hormone (TSH) and free thyroxine (FT4) levels at screening (assessed based on results from the central laboratory)
- 18) Patients meeting any of the following criteria or showing symptoms at screening
 - a) Poorly controlled hypertension (diastolic blood pressure of > 95 mmHg)
 - b) Hypotension with symptoms
 - c) Orthostatic hypotension in which blood pressure after 3 minutes of standing is ≥ 30 mmHg lower for systolic blood pressure or ≥ 20 mmHg lower for diastolic blood pressure, compared with pressures in the supine position before standing
- 19) Patients with a complication of ischemic heart disease, myocardial infarction, or congestive heart failure (irrespective of well or poorly controlled), and patients with a history of angioplasty, stent placement, or coronary artery bypass
- 20) Patients with a history of neuroleptic malignant syndrome or serotonin syndrome
- 21) Patients with a history or complication of epilepsy or epileptic seizures, excluding pediatric febrile seizures, post-traumatic seizures, alcohol withdrawal seizures, and other seizures
- 22) Patients with the following clinical laboratory test values or electrocardiogram (ECG) parameters at screening (assessed based on results from the central laboratory and central ECG measurement facility)
 - a) Platelet count: $\leq 75,000 \, / \text{mm}^3$
 - b) Hemoglobin: $\leq 9 \text{ g/dL}$
 - c) Absolute neutrophil count: ≤ 1000 /mm³

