3.7.3.3 Vital Signs and Physical Examination

(1) Vital signs

(a) Time points

At screening, the initiation and Weeks 1, 4, and 8 (or discontinuation) of the antidepressant treatment period (Phase A), Weeks 1, 2, 3, 4, 5, and 6 (or discontinuation) of the double-blind period (Phase B), and Weeks 1, 2, 3, 4, 5, and 6 (or discontinuation) of the antidepressant-responder treatment-continuation period (Phase A+)

(b) Methods

After keeping the subject in a relaxed state, body temperature will be measured and then blood pressure (systolic and diastolic) and pulse rate will be measured in the supine, sitting, and standing positions in accordance with the measurement methods specified by the trial site. For body temperature, the date and result of measurement will be recorded in the source documents and the CRF. Blood pressure and pulse rate will be measured in the supine, sitting, and standing positions, in this order, after maintaining each position for at least 3 minutes. The date, time, positions, and results of measurement will be recorded in the source documents and the CRF.

(2) Physical examination

(a) Time points

At screening, the initiation and Weeks 1, 2, 3, 4, 6, and 8 (or discontinuation) of the antidepressant treatment period (Phase A), Weeks 1, 2, 3, 4, 5, and 6 (or discontinuation) of the double-blind period (Phase B), post-treatment observation period, and Weeks 1, 2, 3, 4, 5, and 6 (or discontinuation) of the antidepressant-responder treatment-continuation period (Phase A+)

(b) Methods

The investigator or subinvestigator will perform a physical examination that includes the assessment items shown below through subject interview and other relevant methods and record the physical findings in the source documents. The date and results of examinations at screening and only the dates of examinations after the initiation of the antidepressant treatment period (Phase A) will be recorded in the source documents and the CRF. Any clinically significant physical findings compared with findings at screening are to be recorded as AEs.

Assessment items: HEENT (head, eyes, ears, nose, and throat), chest, abdomen, urogenital organs, limbs, nerves, and skin mucosa

(3) Waist circumference

(a) Time points

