7.6.3 Physical Examination and Vital Signs Data

Physical examination data will be provided in a listing.

For each vital sign parameter, descriptive statistics of actual measurements and changes from baseline at each time point will be calculated for each treatment group and for the overall brexpiprazole group.

Numbers and proportions of subjects with potentially clinically significant vital signs will be determined for each treatment group and for the overall brexpiprazole group.

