9.2.1 Adverse Events of Interest

Each adverse event of interest is defined in Appendix 4. Numbers and proportions of subjects with the following AEs of interest will be summarized by SOC and PT by treatment group and for the overall brexpiprazole group.

- Extrapyramidal AEs
- Neuroleptic malignant syndrome-related AEs
- Rhabdomyolysis
- Seizure-related AEs
- Orthostatic disorder-related AEs
- Suicide/suicide attempt-related AEs
- Oversedation-related AEs
- Hypersensitive symptom-related AEs
- Venous thrombosis
- Blood disorder-related AEs
- Glucose metabolism-related AEs
- Lipid metabolism-related AEs
- Body weight-related AEs
- QT interval prolongation-related AEs
- Manic switch-related AEs
- Prolactin increase-related AEs

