9.4 Vital Sign Data

For each vital sign parameter (by position for blood pressure and pulse rate), descriptive statistics of actual measurements and changes from baseline at each time point and the last assessment time point will be calculated for each treatment group and for the overall brexpiprazole group.

Numbers and proportions of subjects with vital signs meeting the criteria for potentially clinically significant vital signs (Appendix 1) will be determined for each treatment group and for the overall brexpiprazole group. A listing of these subjects will be provided.

For each vital sign parameter in the antidepressant treatment period (Phase A), descriptive statistics of actual measurements and changes from baseline (before the start of the antidepressant treatment period [Phase A]) at each time point and the last assessment time point will be calculated overall and for each requisite concomitant medication in the ADT set. A listing of subjects with vital signs meeting the criteria for potentially clinically significant vital signs (Appendix 1) will be provided.

For each vital sign parameter in the antidepressant treatment period (Phase A) and the antidepressant-responder treatment-continuation period (Phase A+), descriptive statistics of actual measurements and changes from baseline (before the start of the antidepressant treatment period [Phase A]) at each time point and the last assessment time point will be calculated overall and for each requisite concomitant medication in the Phase A+ set. A listing of subjects with vital signs meeting the criteria for potentially clinically significant vital signs (Appendix 1) will be provided.

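### SAP Appendix 1's orthostatic row needs a pulse rise and has no diastolic limb, so some postural falls that the protocol calls orthostatic hypotension at entry go uncounted on treatment

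*SAP*

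**What the plan says.** **On treatment.** Protocol 7.6.3 plans that "Numbers and proportions of subjects with potentially clinically significant vital signs will be determined for each treatment group", but gives no numerical criteria. SAP 9.4 takes both the count and the subject listing (CT-11.2 and CT-11.3) from Appendix 1. The orthostatic hypotension row there reads "≥ 20 mmHg decrease in systolic blood pressure and a ≥ 25 bpm increase in pulse rate from supine to sitting/standing". Its change-from-baseline column is marked as not applicable.

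**At entry.** The protocol's only numerical definition of orthostatic hypotension is in exclusion criteria 18c (screening) and 30c (start of Phase A), in the Synopsis and in Table 3.4.3-1. It is a fall from the supine reading to one that "after 3 minutes of standing is ≥ 30 mmHg lower for systolic blood pressure or ≥ 20 mmHg lower for diastolic blood pressure". Pulse is not mentioned.

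**Data.** Protocol 3.7.3.3 states: "Blood pressure and pulse rate will be measured in the supine, sitting, and standing positions, in this order, after maintaining each position"; the minimum is 3 minutes per posture. This is done at Week 8 of Phase A, at Weeks 1 to 6 of Phase B, and at discontinuation.

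**Other outputs.** SAP 9.4 gives descriptive statistics "by position for blood pressure and pulse rate". SAP 9.2.1 lists "Orthostatic disorder-related AEs" among the events of interest (CT-8.9.5). PDATA-8.1 lists vital signs for all randomized subjects.

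**The concern.** One name carries two different rules. The entry rule joins a systolic and a diastolic limb by *or*. The on-treatment rule joins a systolic fall and a pulse rise by *and*, and drops the diastolic limb. A subject can have a postural fall in Phase B that would have excluded them at entry and still not appear in the trial's only categorical count of postural falls in vital signs.

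This is a safety count worth getting right. The Introduction describes the drug as an antagonist at adrenergic alpha-1B receptors, and the SAP makes orthostatic disorders an event of interest. Protocol 4.3 also allows ongoing beta-blockers for cardiovascular disease. Subjects taking them may be less able to raise their pulse by 25 bpm, although the documents do not say how many there will be.

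A second, separate gap is that the row does not exclude subjects who already meet it at baseline. SAP 9.3 applies that exclusion to laboratory values and SAP 9.6 applies it to QTc thresholds; SAP 9.4 has no equivalent. The Phase B entry criteria (9 to 12) do not recheck postural blood pressure, so a fall that arose during Phase A could be counted as a Phase B case.

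**Working it through.** The plan states no figure to reproduce. The check compares the two rules case by case and then looks at whether another planned output fills the gap.

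**Rules**
- Entry (Protocol 18c/30c): systolic fall ≥ 30 **or** diastolic fall ≥ 20, supine to standing.
- On treatment (SAP Appendix 1): systolic fall ≥ 20 **and** pulse rise ≥ 25, supine to sitting or standing.

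**Case by case** (falls in mmHg, pulse rise in bpm)

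| Systolic fall | Diastolic fall | Pulse rise | Entry rule | SAP row |
|---|---|---|---|---|
| 35 | 10 | 10 | met | not met |
| 35 | 10 | 24 | met | not met |
| 35 | 10 | 25 | met | met |
| 25 | 25 | 10 | met | not met |
| 25 | 25 | 30 | met | met |
| 10 | 25 | 30 | met | not met |
| 25 | 10 | 30 | not met | met |

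Three results follow.
1. A fall of entry-rule degree is missed whenever the pulse rise is below 25 bpm.
2. A diastolic-only fall (systolic fall below 20) is missed whatever the pulse does.
3. The last line goes the other way: the SAP row counts a case that the entry rule would not. Neither rule contains the other.

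**Do the other Appendix 1 rows catch the missed cases?** Not necessarily. The low-systolic row needs a value below 90 mmHg and a fall of at least 20 mmHg from baseline. Supine 140 to standing 105 is a fall of 140 − 105 = 35, but 105 is not below 90. The low-diastolic row needs a value below 50 mmHg and a fall of at least 15 mmHg from baseline. Supine 85 to standing 60 is a fall of 85 − 60 = 25, but 60 is not below 50.

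**Do other outputs?** Summaries by position give group statistics for each posture, not a count of subjects whose pressure fell between postures. CT-8.9.5 holds only what was reported as an adverse event, and Protocol 5.2 elicits events with a non-leading question, so a silent fall may not appear. PDATA-8.1 contains the raw readings but no count.

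**Size.** Let *r* be the share of entry-rule falls with a systolic fall of at least 20 mmHg, and *q* the share of those with a pulse rise of at least 25 bpm. The share missed is 1 − *r* × *q*. The documents give neither quantity. Purely as assumptions, *r* = 1.0 with *q* = 0.50 gives 1 − 0.50 = 50%, and *r* = 0.5 with *q* = 0.10 gives 1 − 0.05 = 95%. If *r* and *q* were both 1, it would be 0%. This is a share of readings. SAP 9.4 counts subjects, and a subject has six scheduled Phase B visits with a sitting and a standing comparison at each (6 × 2 = 12), so the share of subjects missed would be lower by an unknown amount.

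**The case against.** The strongest reply is that the two rules serve different purposes. The protocol's thresholds decide who may enter. They are applied at screening and at the start of Phase A, and appear neither in the Phase B entry criteria nor among the withdrawal criteria in Protocol 3.8.3.2. They may describe the degree that excludes a patient and not the trial's definition of the event. Protocol 7.6.3 leaves the on-treatment criteria open and the SAP supplies them. So a reader who infers that the SAP breaches the protocol goes too far: no protocol analysis rule is broken, and SAP section 14 had no change to record.

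Entry limits and on-treatment flags also differ elsewhere: diastolic pressure above 95 against above 105 mmHg, AST and ALT above 2 against at least 3 times the upper limit, fasting glucose at least 126 against at least 100 mg/dL. A different cut-off is not in itself a defect. That stands. Here, though, the difference is one of structure: a condition on a second variable is added and a limb is removed, under the same name and without explanation.

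Two other inferences are tempting and unsupported. One is that all, or most, qualifying subjects are missed. Those with a systolic fall of at least 20 mmHg and a pulse rise of at least 25 bpm are counted, the SAP row is looser in two respects, and any percentage rests on assumption alone. The other is that the comparison between arms is biased. The same row applies in every arm, and nothing in the documents shows a differential effect.

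The baseline gap does not support an undercount either. It adds cases, and because baseline precedes randomization these should balance between arms in expectation.

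Finally, Protocol 1.3 does not list orthostatic hypotension among the important risks, and the overseas depression trials summarised in Protocol 1.2.2 report no marked changes in vital signs. This limits the urgency but does not supply the missing count.

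**Conclusion.** The point holds as an unexplained inconsistency in a safety summary. Subjects whose postural fall is of the degree that the protocol calls orthostatic hypotension at entry are left out of CT-11.2 and CT-11.3 if their pulse rise is below 25 bpm or if the fall is diastolic only. That follows from the definitions and needs no assumption. Raw values and reported events remain available, but no other planned summary counts postural falls.

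The number of subjects affected cannot be determined from the documents. The primary analysis, the type I error rate and the sample size are untouched. Nothing here says which threshold is clinically right. This is a cheap improvement to safety reporting and does not threaten the trial's conclusions on efficacy.

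**What to change.** Before unblinding:

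1. Keep the existing orthostatic row in SAP Appendix 1.
2. Add a supplementary row to Appendix 1, CT-11.2 and CT-11.3 in the protocol's own entry wording: supine to standing, systolic or diastolic limb, no pulse condition.
3. Count the added row only in subjects who do not meet it at Week 8 of Phase A, in line with the approach of SAP 9.3 and 9.6. Mark it as a Phase B row, because Appendix 1 also feeds the Phase A and Phase A+ listings.
4. State in the SAP why the entry definition and the existing on-treatment row differ, without asserting that either threshold is the clinically correct one.

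**Cost.** SAP wording, one table row and one listing. No new data are needed, because supine and standing pressures are already taken at Week 8 of Phase A and at every Phase B visit. The downside is a higher reported count that will include some asymptomatic falls.

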Appendix 2 Criteria for Identifying Laboratory Values of Potential Clinical Relevance

Laboratory Tests		Criteria
Chemistry		
AST (SGOT)		$\geq 3 \times$ upper limit of normal (ULN)
ALT (SGPT)		$\geq 3 \times$ ULN
Alkaline phosphatase		$\geq 3 \times$ ULN
LDH		$\geq 3 \times$ ULN
BUN		$\geq 30 \text{ mg/dL}$
Creatinine		$\geq 2.0 \text{ mg/dL}$
Uric Acid		
Men		$\geq 10.5 \text{ mg/dL}$
Women		$\geq 8.5 \text{ mg/dL}$
Bilirubin (total)		$\geq 2.0 \text{ mg/dL}$
CPK		$\geq 3 \times$ ULN
Endocrinology		
Prolactin		$>$ ULN
Hematology		
Hematocrit		
Men		$\leq 37\%$ and decrease of ≥ 3 percentage points from Baseline
Women		$\leq 32\%$ and decrease of ≥ 3 percentage points from Baseline
Hemoglobin		
Men		$\leq 11.5 \text{ g/dL}$
Women		$\leq 9.5 \text{ g/dL}$
White blood count		$\leq 2,800/\text{mm}^3$ or $\geq 16,000/\text{mm}^3$
Eosinophils		$\geq 10\%$
Neutrophils		$\leq 15\%$
Absolute neutrophil count		$\leq 1,000/\text{mm}^3$
Platelet count		$\leq 75,000/\text{mm}^3$ or $\geq 700,000/\text{mm}^3$
Urinalysis		
Protein		Increase of ≥ 2 units
Glucose		Increase of ≥ 2 units
Additional Criteria		
Chloride		$\leq 90 \text{ mEq/L}$ or $\geq 118 \text{ mEq/L}$
Potassium		$\leq 2.5 \text{ mEq/L}$ or $\geq 6.5 \text{ mEq/L}$
Sodium		$\leq 126 \text{ mEq/L}$ or $\geq 156 \text{ mEq/L}$
Calcium		$\leq 8.2 \text{ mg/dL}$ or $\geq 12 \text{ mg/dL}$
Glucose		
Fasting		$\geq 100 \text{ mg/dL}$
Non-Fasting		$\geq 200 \text{ mg/dL}$
Total Cholesterol, Fasting		$\geq 240 \text{ mg/dL}$
LDL Cholesterol, Fasting		$\geq 160 \text{ mg/dL}$
HDL Cholesterol, Fasting		
Men		$< 40 \text{ mg/dL}$
Women		$< 50 \text{ mg/dL}$
Triglycerides, Fasting		$\geq 150 \text{ mg/dL}$

Appendix 3 Criteria for Identifying ECG Measurements of Potential Clinical Relevance

Variable	Criterion Value ^a	Change Relative to Baseline ^a
Heart Rate	≥ 120 bpm	increase of ≥ 15 bpm
	≤ 50 bpm	decrease of ≥ 15 bpm
PR	≥ 200 msec	increase of ≥ 50 msec
QRS	≥ 120 msec	increase of ≥ 20 msec
QTcF	> 450 msec (males and females)	

^aIn order to be identified as potentially clinically relevant, an on-treatment value must meet the “Criterion Value” and also represent a change from the subject’s baseline value of at least the magnitude shown in the “Change Relative to Baseline” column.

Appendix 4 Adverse Events of Interest

AE Category	Preferred Term
EFFECT ON GLUCOSE	Blood glucose abnormal Blood glucose increased Diabetes mellitus Diabetes mellitus inadequate control Diabetes with hyperosmolarity Diabetic coma Diabetic hyperglycaemic coma Diabetic hyperosmolar coma Diabetic ketoacidosis Diabetic ketoacidotic hyperglycaemic coma Glucose tolerance decreased Glucose tolerance impaired Glucose tolerance test abnormal Glucose urine present Glycosuria Glycosylated haemoglobin increased Hyperglycaemia Hyperglycaemic hyperosmolar nonketotic syndrome Impaired fasting glucose Increased insulin requirement Indeterminate glucose tolerance Insulin resistance Insulin resistant diabetes Insulin tolerance test abnormal Insulin-requiring type 2 diabetes mellitus Ketoacidosis Ketonuria Ketosis Metabolic syndrome Type 1 diabetes mellitus Type 2 diabetes mellitus Urine ketone body present
EFFECT ON LIPIDS	3-hydroxyacetyl-coenzyme A dehydrogenase deficiency Acquired mixed hyperlipidaemia Apolipoprotein Apolipoprotein A-I Apolipoprotein A-I abnormal Apolipoprotein A-I decreased Apolipoprotein A-I increased Apolipoprotein A-I normal Apolipoprotein A-II Apolipoprotein A-II abnormal Apolipoprotein A-II decreased Apolipoprotein A-II increased Apolipoprotein A-II normal Apolipoprotein B Apolipoprotein B abnormal Apolipoprotein B decreased Apolipoprotein B increased

Apolipoprotein B normal
Apolipoprotein B/Apolipoprotein A-1 ratio
Apolipoprotein B/Apolipoprotein A-1 ratio increased
Apolipoprotein C
Apolipoprotein C abnormal
Apolipoprotein E
Apolipoprotein E abnormal
Apolipoprotein E increased
Apolipoprotein abnormal
Apolipoprotein decreased
Apolipoprotein increased
Apolipoprotein normal
Autoimmune hyperlipidaemia
Barth syndrome
Blood cholesterol
Blood cholesterol abnormal
Blood cholesterol decreased
Blood cholesterol esterase increased
Blood cholesterol increased
Blood cholesterol normal
Blood triglycerides
Blood triglycerides abnormal
Blood triglycerides decreased
Blood triglycerides increased
Blood triglycerides normal
Body fat disorder
CANDLE syndrome
Cardiac steatosis
Carnitine
Carnitine abnormal
Carnitine decreased
Carnitine deficiency
Carnitine increased
Carnitine normal
Carnitine palmitoyltransferase deficiency
Carnitine-acylcarnitine translocase deficiency
Cholesterol absorption efficiency decreased
Cholesterosis
Chylomircron decreased
Chylomircron increased
Chylomircrons
Congenital carnitine deficiency
Dyslipidaemia
Epidural lipomatosis
Facial wasting
Familial high density lipoprotein deficiency
Familial hypertriglyceridaemia
Fat redistribution
Fatty acid deficiency
Fatty acid oxidation disorder
Fatty liver alcoholic
Free fatty acids
Free fatty acids abnormal

Free fatty acids decreased
Free fatty acids increased
Gastric xanthoma
HIV lipodystrophy
Hepatic steato-fibrosis
Hepatic steatosis
High density lipoprotein
High density lipoprotein abnormal
High density lipoprotein decreased
High density lipoprotein increased
High density lipoprotein normal
Hyper HDL cholesterolaemia
Hypercholesterolaemia
Hyperchylomicronaemia
Hyperlipidaemia
Hypertriglyceridaemia
Hypo HDL cholesterolaemia
Hypocarnitinaemia
Hypocholesterolaemia
Hypolipidaemia
Hypotriglyceridaemia
Inborn error of lipid metabolism
Intermediate density lipoprotein decreased
Intermediate density lipoprotein increased
Intestinal lipomatosis
Intestinal steatosis
LDL/HDL ratio
LDL/HDL ratio decreased
LDL/HDL ratio increased
Lecithin-cholesterol acyltransferase activity decreased
Lecithin-cholesterol acyltransferase activity increased
Lecithin-cholesterol acyltransferase deficiency
Lipaemia retinalis
Lipaemic index score
Lipid metabolism disorder
Lipid proteinosis
Lipids
Lipids abnormal
Lipids decreased
Lipids increased
Lipids normal
Lipoatrophy
Lipodystrophy acquired
Lipoedema
Lipohypertrophy
Lipomatosis
Lipoprotein (a)
Lipoprotein (a) abnormal
Lipoprotein (a) decreased
Lipoprotein (a) increased
Lipoprotein (a) normal
Lipoprotein abnormal
Lipoprotein deficiency

Lipoprotein increased
Long-chain acyl-coenzyme A dehydrogenase deficiency
Low density lipoprotein
Low density lipoprotein abnormal
Low density lipoprotein decreased
Low density lipoprotein increased
Low density lipoprotein normal
Medium-chain acyl-coenzyme A dehydrogenase deficiency
Mesangiolipidosis
Non-alcoholic steatohepatitis
Non-high-density lipoprotein cholesterol
Non-high-density lipoprotein cholesterol decreased
Non-high-density lipoprotein cholesterol increased
Nonalcoholic fatty liver disease
Pancreatic steatosis
Parotid lipomatosis
Partial lipodystrophy
Phospholipidosis
Phytanic acid increased
Phytosterol level
Phytosterol level increased
Phytosterolaemia
Primary hypercholesterolaemia
Remnant hyperlipidaemia
Remnant-like lipoprotein particles
Remnant-like lipoprotein particles increased
Renal lipomatosis
Renal phospholipidosis
Serum pristanic acid increased
Short-chain acyl-coenzyme A dehydrogenase deficiency
Steatohepatitis
Tangier disease
Thyroid steatosis
Total cholesterol/HDL ratio
Total cholesterol/HDL ratio abnormal
Total cholesterol/HDL ratio decreased
Total cholesterol/HDL ratio increased
Total cholesterol/HDL ratio normal
Trifunctional protein deficiency
Type I hyperlipidaemia
Type II hyperlipidaemia
Type III hyperlipidaemia
Type IIa hyperlipidaemia
Type IIb hyperlipidaemia
Type IV hyperlipidaemia
Type V hyperlipidaemia
Very long-chain acyl-coenzyme A dehydrogenase deficiency
Very low density lipoprotein
Very low density lipoprotein abnormal
Very low density lipoprotein decreased
Very low density lipoprotein increased
Very low density lipoprotein normal
Xanthelasma

EFFECTS ON WEIGHT

EPS

Xanthoma
 Xanthomatosis
 Zieve syndrome
 Abnormal weight gain
 Body mass index abnormal
 Body mass index increased
 Obesity
 Overweight
 Waist circumference increased
 Weight fluctuation
 Weight increased
 Abnormal involuntary movement scale
 Action tremor
 Akathisia
 Akinesia
 Asterixis
 Athetosis
 Ballismus
 Blepharospasm
 Bradykinesia
 Bradyphrenia
 Buccoglossal syndrome
 Chorea
 Choroathetosis
 Chronic tic disorder
 Clumsiness
 Cogwheel rigidity
 Complex tic
 Dopamine dysregulation syndrome
 Drooling
 Dysarthria
 Dyskinesia
 Dyskinesia neonatal
 Dyskinesia oesophageal
 Dyslalia
 Dysphonia
 Dystonia
 Dystonic tremor
 Emprosthotonus
 Essential tremor
 Excessive eye blinking
 Extrapyramidal disorder
 Facial spasm
 Fine motor skill dysfunction
 Freezing phenomenon
 Fumbling
 Gait disturbance
 Gait inability
 Gaze palsy
 Glabellar reflex abnormal
 Grimacing
 Head titubation
 Huntington's disease

Hyperkinesia
Hyperkinesia neonatal
Hypertonia
Hypertonia neonatal
Hypokinesia
Hypokinesia neonatal
Hypokinetic dysarthria
Intention tremor
Laryngeal tremor
Laryngospasm
Meige's syndrome
Micrographia
Mobility decreased
Motor dysfunction
Movement disorder
Muscle contractions involuntary
Muscle contracture
Muscle rigidity
Muscle spasms
Muscle spasticity
Muscle tightness
Muscle tone disorder
Muscle twitching
Musculoskeletal stiffness
Myoclonus
Myotonia
Nuchal rigidity
Oculogyric crisis
Oesophageal spasm
On and off phenomenon
Opisthotonus
Oromandibular dystonia
Oropharyngeal spasm
Parkinson's disease
Parkinson's disease psychosis
Parkinsonian crisis
Parkinsonian gait
Parkinsonian rest tremor
Parkinsonism
Parkinsonism hyperpyrexia syndrome
Periodic limb movement disorder
Pharyngeal dyskinesia
Pharyngeal dystonia
Pleurothotonus
Postural reflex impairment
Postural tremor
Posture abnormal
Posturing
Propulsive gait
Protrusion tongue
Provisional tic disorder
Psychomotor hyperactivity
Rabbit syndrome

Reduced facial expression
Respiratory dyskinesia
Resting tremor
Restless legs syndrome
Restlessness
Risus sardonicus
Saliva altered
Salivary hypersecretion
Secondary tic
Spasmodic dysphonia
Tardive dyskinesia
Tic
Tongue paralysis
Tongue spasm
Torticollis
Torticollis psychogenic
Tremor
Tremor neonatal
Trismus
Uvular spasm
Walking disability
Writer's cramp
5q minus syndrome
ABO haemolytic disease of newborn
ABO incompatibility
ADAMTS13 activity abnormal
ADAMTS13 activity assay
ADAMTS13 activity decreased
ADAMTS13 activity increased
ADAMTS13 activity normal
ADAMTS13 inhibitor screen assay
Aase syndrome
Abdominal lymphadenopathy
Abnormal clotting factor
Accessory spleen
Acid haemolysin test
Acid haemolysin test negative
Acid haemolysin test positive
Acquired Von Willebrand's disease
Acquired amegakaryocytic thrombocytopenia
Acquired antithrombin III deficiency
Acquired asplenia
Acquired complement deficiency disease
Acquired dysfibrinogenaemia
Acquired factor IX deficiency
Acquired factor VIII deficiency
Acquired factor XI deficiency
Acquired haemoglobinopathy
Acquired haemophilia
Acquired protein S deficiency
Acquired thalassaemia
Acral angiokeratoma-like pseudolymphoma
Activated partial thromboplastin time

Activated partial thromboplastin time abnormal
Activated partial thromboplastin time normal
Activated partial thromboplastin time prolonged
Activated partial thromboplastin time ratio
Activated partial thromboplastin time ratio abnormal
Activated partial thromboplastin time ratio decreased
Activated partial thromboplastin time ratio fluctuation
Activated partial thromboplastin time ratio increased
Activated partial thromboplastin time ratio normal
Activated partial thromboplastin time shortened
Activated protein C resistance
Activated protein C resistance test
Activated protein C resistance test positive
Acute bilineal leukaemia
Acute biphenotypic leukaemia
Acute chest syndrome
Acute erythroid leukaemia
Acute febrile neutrophilic dermatosis
Acute haemolytic transfusion reaction
Acute haemorrhagic oedema of infancy
Acute leukaemia
Acute leukaemia in remission
Acute lymphocytic leukaemia
Acute lymphocytic leukaemia (in remission)
Acute lymphocytic leukaemia recurrent
Acute lymphocytic leukaemia refractory
Acute megakaryocytic leukaemia
Acute megakaryocytic leukaemia (in remission)
Acute monocytic leukaemia
Acute monocytic leukaemia (in remission)
Acute myeloid leukaemia
Acute myeloid leukaemia (in remission)
Acute myeloid leukaemia recurrent
Acute myeloid leukaemia refractory
Acute myelomonocytic leukaemia
Acute promyelocytic leukaemia
Acute undifferentiated leukaemia
Adenoiditis
Administration site lymphadenopathy
Adult T-cell lymphoma/leukaemia
Adult T-cell lymphoma/leukaemia recurrent
Adult T-cell lymphoma/leukaemia refractory
Adult T-cell lymphoma/leukaemia stage I
Adult T-cell lymphoma/leukaemia stage II
Adult T-cell lymphoma/leukaemia stage III
Adult T-cell lymphoma/leukaemia stage IV
Agranulocytosis
Aleukaemic leukaemia
Allergic bronchopulmonary mycosis
Allergic eosinophilia
Alloimmunisation
Alpha-thalassaemia-intellectual deficit syndrome
A megakaryocytic thrombocytopenia

Anaemia
Anaemia Heinz body
Anaemia folate deficiency
Anaemia macrocytic
Anaemia megaloblastic
Anaemia neonatal
Anaemia of chronic disease
Anaemia of malignant disease
Anaemia of pregnancy
Anaemia postoperative
Anaemia splenic
Anaemia vitamin B12 deficiency
Anaemia vitamin B6 deficiency
Anaemic hypoxia
Anaphylactoid syndrome of pregnancy
Anaplastic large cell lymphoma T- and null-cell types
Anaplastic large cell lymphoma T- and null-cell types recurrent
Anaplastic large cell lymphoma T- and null-cell types refractory
Anaplastic large cell lymphoma T- and null-cell types stage I
Anaplastic large cell lymphoma T- and null-cell types stage II
Anaplastic large cell lymphoma T- and null-cell types stage III
Anaplastic large cell lymphoma T- and null-cell types stage IV
Anaplastic large-cell lymphoma
Angiocentric lymphoma
Angiocentric lymphoma recurrent
Angiocentric lymphoma refractory
Angiocentric lymphoma stage I
Angiocentric lymphoma stage II
Angiocentric lymphoma stage III
Angiocentric lymphoma stage IV
Angioimmunoblastic T-cell lymphoma
Angioimmunoblastic T-cell lymphoma recurrent
Angioimmunoblastic T-cell lymphoma refractory
Angioimmunoblastic T-cell lymphoma stage I
Angioimmunoblastic T-cell lymphoma stage II
Angioimmunoblastic T-cell lymphoma stage III
Angioimmunoblastic T-cell lymphoma stage IV
Angiolympoid hyperplasia with eosinophilia
Anisochromia
Anisocytosis
Anti A antibody
Anti A antibody positive
Anti B antibody
Anti B antibody positive
Anti Kell antibody test
Anti Kell antibody test negative
Anti Kell antibody test positive
Anti factor IX antibody
Anti factor IX antibody increased
Anti factor IX antibody negative
Anti factor IX antibody positive
Anti factor V antibody
Anti factor V antibody positive

Anti factor VII antibody positive
Anti factor VIII antibody increased
Anti factor VIII antibody negative
Anti factor VIII antibody positive
Anti factor VIII antibody test
Anti factor X activity
Anti factor X activity abnormal
Anti factor X activity decreased
Anti factor X activity increased
Anti factor X activity normal
Anti factor X antibody
Anti factor X antibody negative
Anti factor X antibody positive
Anti factor XI antibody positive
Anti factor XII antibody positive
Anti factor Xa activity decreased
Anti factor Xa assay normal
Anti-complement antibody
Anti-erythropoietin antibody
Anti-erythropoietin antibody negative
Anti-erythropoietin antibody positive
Anti-prothrombin antibody positive
Anti-thrombin antibody
Antiphospholipid syndrome
Antithrombin III
Antithrombin III abnormal
Antithrombin III decreased
Antithrombin III deficiency
Antithrombin III increased
Aplasia pure red cell
Aplastic anaemia
Application site lymphadenopathy
Aspiration bone marrow
Aspiration bone marrow abnormal
Aspiration bone marrow normal
Asplenia
Atypical haemolytic uraemic syndrome
Atypical lymphocytic lobular panniculitis
Atypical mycobacterial lymphadenitis
Autoimmune anaemia
Autoimmune aplastic anaemia
Autoimmune haemolytic anaemia
Autoimmune heparin-induced thrombocytopenia
Autoimmune lymphoproliferative syndrome
Autoimmune neutropenia
Autoimmune pancytopenia
Autosomal recessive megaloblastic anaemia
Axillary web syndrome
B precursor type acute leukaemia
B-cell aplasia
B-cell lymphoma
B-cell lymphoma recurrent
B-cell lymphoma refractory

B-cell lymphoma stage I
B-cell lymphoma stage II
B-cell lymphoma stage III
B-cell lymphoma stage IV
B-cell prolymphocytic leukaemia
B-cell small lymphocytic lymphoma
B-cell small lymphocytic lymphoma recurrent
B-cell small lymphocytic lymphoma refractory
B-cell small lymphocytic lymphoma stage I
B-cell small lymphocytic lymphoma stage II
B-cell small lymphocytic lymphoma stage III
B-cell small lymphocytic lymphoma stage IV
B-cell type acute leukaemia
B-cell unclassifiable lymphoma high grade
B-cell unclassifiable lymphoma low grade
B-lymphocyte abnormalities
B-lymphocyte count
B-lymphocyte count abnormal
B-lymphocyte count decreased
B-lymphocyte count increased
Babesiosis
Band neutrophil count
Band neutrophil count decreased
Band neutrophil count increased
Band neutrophil percentage
Band neutrophil percentage decreased
Band neutrophil percentage increased
Bandaemia
Banti's syndrome
Basophil count
Basophil count abnormal
Basophil count decreased
Basophil count increased
Basophil count normal
Basophil morphology
Basophil morphology abnormal
Basophil morphology normal
Basophil percentage
Basophil percentage decreased
Basophil percentage increased
Basophilia
Basophilopenia
Benign ethnic neutropenia
Benign lymph node neoplasm
Benign neoplasm of thymus
Benign spleen tumour
Benjamin syndrome
Bernard-Soulier syndrome
Beta globin abnormal
Bicytopenia
Bing-Neel syndrome
Biopsy bone marrow
Biopsy bone marrow abnormal

Biopsy bone marrow normal
Biopsy lymph gland
Biopsy lymph gland abnormal
Biopsy lymph gland normal
Biopsy spleen
Biopsy spleen abnormal
Biopsy spleen normal
Biopsy thymus gland
Biopsy thymus gland abnormal
Biopsy thymus gland normal
Blackwater fever
Blast cell count decreased
Blast cell count increased
Blast cell crisis
Blast cell proliferation
Blast cells
Blast cells absent
Blast cells present
Blast crisis in myelogenous leukaemia
Blastic plasmacytoid dendritic cell neoplasia
Bleeding time
Bleeding time abnormal
Bleeding time normal
Bleeding time prolonged
Bleeding time shortened
Blood count
Blood count abnormal
Blood count normal
Blood disorder
Blood erythropoietin
Blood erythropoietin abnormal
Blood erythropoietin decreased
Blood erythropoietin increased
Blood erythropoietin normal
Blood fibrinogen
Blood fibrinogen abnormal
Blood fibrinogen decreased
Blood fibrinogen increased
Blood fibrinogen normal
Blood group A
Blood group AB
Blood group B
Blood group O
Blood grouping
Blood incompatibility haemolytic anaemia of newborn
Blood loss anaemia
Blood loss anaemia neonatal
Blood loss assessment
Blood thrombin
Blood thrombin abnormal
Blood thrombin decreased
Blood thrombin increased
Blood thrombin normal

Blood thromboplastin
Blood thromboplastin abnormal
Blood thromboplastin decreased
Blood thromboplastin increased
Blood thromboplastin normal
Blood type incompatibility
Blood viscosity abnormal
Blood viscosity decreased
Blood viscosity increased
Bone marrow band neutrophil count increased
Bone marrow basophilic leukocyte count increased
Bone marrow disorder
Bone marrow eosinophilic leukocyte count increased
Bone marrow failure
Bone marrow granuloma
Bone marrow haemorrhage
Bone marrow infiltration
Bone marrow ischaemia
Bone marrow leukaemic cell infiltration
Bone marrow metamyelocyte count increased
Bone marrow myelogram
Bone marrow myelogram abnormal
Bone marrow myelogram normal
Bone marrow necrosis
Bone marrow oedema
Bone marrow oedema syndrome
Bone marrow plasmacyte count increased
Bone marrow polymorphonuclear leukocyte count increased
Bone marrow reticulin fibrosis
Bone marrow transplant rejection
Bone marrow tumour cell infiltration
Breakthrough haemolysis
Breast implant-associated anaplastic large cell lymphoma
Broncholithiasis
Bronchopulmonary aspergillosis allergic
Burkitt's leukaemia
Burkitt's lymphoma
Burkitt's lymphoma recurrent
Burkitt's lymphoma refractory
Burkitt's lymphoma stage I
Burkitt's lymphoma stage II
Burkitt's lymphoma stage III
Burkitt's lymphoma stage IV
CANDLE syndrome
CD4 lymphocyte percentage decreased
CD4 lymphocyte percentage increased
CD4 lymphocytes
CD4 lymphocytes abnormal
CD4 lymphocytes decreased
CD4 lymphocytes increased
CD4 lymphocytes normal
CD4/CD8 ratio
CD4/CD8 ratio decreased

CD4/CD8 ratio increased
CD8 lymphocyte percentage decreased
CD8 lymphocyte percentage increased
CD8 lymphocytes
CD8 lymphocytes abnormal
CD8 lymphocytes decreased
CD8 lymphocytes increased
Capillary fragility abnormal
Capillary fragility decreased
Capillary fragility increased
Capillary fragility normal
Capillary fragility test
Capillary permeability
Capillary permeability increased
Capillary permeability normal
Carboxyhaemoglobinæmia
Cardiac haemolytic anaæmia
Cardiac lymphangioma
Castleman's disease
Central nervous system leukaæmia
Central nervous system lymphoma
Chediak-Higashi syndrome
Chloroma
Chloroma (in remission)
Chorea-acanthocytosis
Chronic eosinophilic leukaæmia
Chronic granulomatous disease
Chronic leukaæmia
Chronic leukaæmia in remission
Chronic lymphocytic leukaæmia
Chronic lymphocytic leukaæmia (in remission)
Chronic lymphocytic leukaæmia recurrent
Chronic lymphocytic leukaæmia refractory
Chronic lymphocytic leukaæmia stage 0
Chronic lymphocytic leukaæmia stage 1
Chronic lymphocytic leukaæmia stage 2
Chronic lymphocytic leukaæmia stage 3
Chronic lymphocytic leukaæmia stage 4
Chronic lymphocytic leukaæmia transformation
Chronic myeloid leukaæmia
Chronic myeloid leukaæmia (in remission)
Chronic myeloid leukaæmia recurrent
Chronic myeloid leukaæmia transformation
Chronic myelomonocytic leukaæmia
Chronic myelomonocytic leukaæmia (in remission)
Chronic myelomonocytic leukaæmia with N-ras gene mutation
Chronic pigmented purpura
Circulating anticoagulant
Circulating anticoagulant positive
Clonal haematopoiesis
Clot retraction
Clot retraction abnormal
Clot retraction normal

Clot retraction time prolonged
Clot retraction time shortened
Coagulation disorder neonatal
Coagulation factor
Coagulation factor IX level
